## 4.3 Inclusion of Women and Minorities

Both men and women and members of all races and ethnic groups will be eligible for this trial. However, given that the distribution of the Italian population mainly consists of white Caucasians (about 93%), we expect very few subjects of different ethnic background to be enrolled in the screening. The gender distribution among the Cosmos 2 screening population is about 65% and 35% for men and women, respectively and we expect a similar distribution in the chemoprevention study. Detailed information about distribution is reported in the DCP Protocol Submission Worksheet (PSW).

## 4.4 Recruitment and Retention Plan

The projected number of eligible subjects in the entire cohort of 8,000 individuals undergoing annual screening at EIO will be close to 600. Considering that 20% of subjects will be excluded because of ongoing treatment with Aspirin, the eligible pool will include about 480 subjects. Accrual rate is expected to be no less than 32% of the predicted pool. This percentage is higher than the average recruitment rate in chemoprevention trials in healthy subjects (average 10%), but is reasonable given that the population is represented by highly motivated volunteers and previous EIO screening compliance has been higher than 97%. This would allow to consent about 150 people, whose slides will be re-reviewed and re-measured by a study dedicated radiologist and pulmonologist. It is expected that approximately 128, or 80% of consented individuals, will meet all eligibility criteria for the protocol and will be randomized. Since the Cosmos 2 trial is a five year protocol with annual low-dose CT scans, we will have the opportunity to pre-screen the individuals participating in the Cosmos trial for eligibility and to approach them with the present protocol at the time of their next scheduled Cosmos trial-directed CT scan that falls within the window of our trial accrual period. Additionally, there will be individuals who develop new small nodules for the first time while participating in the Cosmos protocol. Such individuals will return per Cosmos protocol for a repeat CT scan in 3 months, and if they meet the inclusion criteria of the present trial after the repeat CT scan, they will also be captured.

MDACC launched its Lung Cancer Screening Program in 2011. To date, nearly 800 participants have been screened averaging approximately 20-30 screened participants per month. An additional resource for screening CTs is the active protocol entitled *“Biospecimen Banking and Biomarker Validation for Lung Cancer Early Detection in Cohort Receiving Low Dose Helical Computed Tomography Screening”* which has 194 participants currently enrolled. Although literature indicates the frequency of eligible lesions is approximately 30%, MDACC’s experience is slightly less at 10% (2-3 participants per month) identified by low dose screening CT scan. From this population, it is anticipated the Lung Cancer Screening program may enroll approx. 1 eligible participant per month after evaluation of other eligibility criteria. However, with the inclusion of lesions identified by diagnostic CT scan, MDACC’s large cancer survivor population offers a larger pool of potentially eligible participants undergoing CTs for surveillance.

### *Pre-Initiation phase*

Both at IEO and MDACC, subjects with persistent subsolid lung nodules detected during any of the screening programs are potentially eligible for the trial and will be identified as potential candidates for the study by the local Lung Cancer Screening program coordinator. In addition, subjects with subsolid lesions identified outside the context of a screening program will be indicated to the research staff by the collaborating radiologists creating a future recruitment resource. While waiting for the subsequent CT scan, the potential candidate will be given a leaflet about the possibility of being contacted for taking part in a prevention trial.

### *Active Recruitment phase*

At EIO, after the evaluation of the CT scan by the radiologist and the thoracic surgeon (Co-PI), and the verification of all inclusion criteria, the potential candidate will be contacted by the staff of the Division of Cancer Prevention and Genetics for the first phone interview. Each subject will be given a unique and consecutive ID number (four digits). The trial design will be explained and availability to participate will be asked. Candidates accepting to participate or interested in the study will be invited for a visit at EIO for informed consent and baseline visit.

At MDACC, after the evaluation of the CT scan by the thoracic radiologist (Co-PI), and the verification of all inclusion criteria, the potential participant will be contacted by the MDACC staff for the first phone

interview. The study design, treatment plan, procedures, follow-up schedule, risks, side effects and potential benefits will be discussed with the potential participants. Interested participants will be scheduled for informed consent and baseline visits in the Cancer Prevention Center. Each subject will be given a unique and consecutive ID number (four digits).

*Retention phase (which include adherence strategies)*

The retention phase will be identical between EIO and MD Anderson. Participants will be scheduled for periodic clinic visits (at 0, 6 and 12 months) during which a complete physical exam and lab tests will be performed. At months 1, 3 and 9 subjects will be contacted by phone to evaluate self-reported compliance/adherence to the treatment and toxicity. In addition they will be reminded about the visit, CT scan and blood and urine samples at month 6 and 12.

Recruitment and retention effort will be evaluated routinely by the site coordinator and the study staff. It can be modified as necessary to promote rapid accrual and to assure maximally high retention rate of participants.

## **5. AGENT ADMINISTRATION**

Drug will be administered on an outpatient basis. Reported adverse events and potential risks are described in Section 6.2.

### **5.1 Dose Regimen and Dose Groups**

Group 1

Agent: Aspirin

Daily doses: one dose of 100 mg once a day

Duration: one year

Group 2

Agent: placebo

Daily doses: one dose once a day

Duration: one year

### **5.2 Aspirin Administration**

At EIO, [name] (PI) will be responsible for drug administration. He can delegate the colleagues of the Division of Cancer Prevention and Genetics (MDs and research nurses) to administer the agent on his behalf.

At MD Anderson, [name] (MD Anderson Site PI) will be responsible for drug administration. She can delegate to MDACC site collaborators to administer agent on her behalf as noted in the Delegation of Authority log.

Subjects will receive a 7-month supply of the drug/placebo as outlined in the clinical procedure schema (see paragraph 7.1. for a detailed description). Each kit contains of 210 tablets (7 bottles of 30 tablets each) of aspirin 100 mg or placebo.

Subjects will be advised to take aspirin after food.

### 5.3 Run-in Procedures

No run-in procedure will take place in the present protocol.

### 5.4 Contraindications

Aspirin should not be taken by people who are allergic to ibuprofen or naproxen, or who have salicylate intolerance or a more generalized drug intolerance to non-steroidal anti-inflammatory drugs (NSAIDs), and caution should be exercised in those with asthma or NSAID-precipitated bronchospasm. Owing to its effect on the stomach lining, manufacturers recommend people with peptic ulcers, mild diabetes, or gastritis seek medical advice before using aspirin. Even if none of these conditions is present, the risk of stomach bleeding is still increased when aspirin is taken with alcohol or warfarin. Patients with hemophilia or other bleeding tendencies should not take aspirin or other salicylates. Aspirin is known to cause haemolytic anemia in people who have the genetic disease glucose-6-phosphate dehydrogenase deficiency, particularly in large doses and depending on the severity of the disease. People with kidney disease, hyperuricemia, or gout should not take aspirin because it inhibits the kidneys' ability to excrete uric acid, and thus may exacerbate these conditions.

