## 4.2 Exclusion Criteria

4.2.1 Subjects with chronic treatment (at least twice/week for more than 3 months) with Aspirin or other NSAIDs.

4.2.2 History of allergic reactions attributed to compounds of similar chemical or biological composition to aspirin, NSAIDs, COX2 inhibitors.

4.2.3 Invasive malignancy (with the exclusion of basal cell carcinoma or skin squamous cell carcinoma) diagnosed during the last 2 years before randomization; stage I-II invasive malignancies that were diagnosed more than 2 years prior to randomization and have been treated curatively are allowed as long as all treatment is finished at least 18 months prior to randomization.

4.2.4 History of therapeutic doses of anticoagulants including warfarin and low molecular weight Heparin (e.g. for prior deep venous thrombosis and pulmonary embolisms) in the preceding year.

4.2.5 Uncontrolled intercurrent illness including, but not limited to, ongoing or active infection, symptomatic congestive heart failure, unstable angina pectoris, cardiac arrhythmia, or psychiatric illness/social situations that would limit compliance with study requirements.

4.2.6 Pregnant women are excluded from this study because Aspirin is an agent with the potential for teratogenic or abortifacient effects. Because there is an unknown but potential risk for adverse events in nursing infants secondary to treatment of the mother with Aspirin, breastfeeding should be discontinued if the mother is treated with Aspirin.

4.2.7 Individual may not be receiving any other investigational agents, antiplatelet agents (e.g. aspirin, clopidogrel (plavix or others)), anticoagulants (e.g. heparin or heparinoids, coumadin, or others), metotrexate, lithium.

4.2.8 Participants with bleeding diathesis, history of gastric/duodenal ulcers in the last 5 years, NSAID-precipitated bronchospasm, patients unwilling or unable to limit alcohol consumption to i.e.  $\leq 3$  alcohol drinks a day.

4.2.9 Participants who in the opinion of the PI will be at higher risk of ASA-related complications.

4.2.10 Participants with known inability to adequately absorb oral medication.

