### 5.5 Concomitant Medications

Other NSAIDs or glucocorticosteroids should be avoided or limited. Any use of systemic or topic NSAIDs or glucocorticosteroids should be clearly documented (time, doses, routes, indications) and followed regularly.

If a participant requires pain relievers or antipyretics, the use of non-NSAIDs, e.g., acetaminophen, should be encouraged. It is not necessary to break the blind in most situations. A protonic pump inhibitor (PPI, omeprazole 20 mg/day tablet) will be added during the period of any NSAIDs or glucocorticosteroids treatment and will be stopped once NSAIDs or glucocorticosteroids are withdrawn.

Short courses of systemic NSAIDs or glucocorticosteroids (defined as up to 2 weeks at a time) are allowed. No more than 1 month total of off-protocol NSAIDs or glucocorticosteroids is allowed in a 6 months period. If it is anticipated that continuous NSAIDs or glucocorticosteroids will be needed or if more than 1 month of NSAIDs or glucocorticosteroids occurs during a 6 months period, the participant will stop study drug. However, since the participant will still undergo his/her yearly scan, they can still be assessed in an intent-to-treat analysis and thus do not come off the study. Non systemic glucocorticosteroids use is allowed without time restrictions.

All medications (prescription and over-the-counter), vitamin and mineral supplements, and/or herbs taken by the participant will be documented on the concomitant medication CRF and will include: 1) start and stop date, dose and route of administration, and indication. Medications taken for a procedure (e.g., biopsy) should also be included.

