### *Randomization:*

Participants will be assigned a randomization number once the following has been accomplished: eligibility has been verified at the site level, eligibility has been confirmed by the site PI, and eligibility CRF has been entered into the DMI web application. The randomization number will be generated by the database and assigned to the participant. Refer to Section 13.2 for details of randomization.

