#### Baseline and Randomization:

- Signed informed consent.

- Collection of a blood samples (safety including  $\beta$ -HCG if applicable, biomarkers including TXB2 and biorepository), urine samples (biomarkers), physical exam and medical history including baseline symptoms; concomitant medications; confirmation of eligibility criteria
- Participants are randomized to receive either study agent or placebo and will be given a 7-month supply of drug or placebo (a kit containing 7 bottles of drug or placebo, with 30 tablets in each bottle, 1 tablet per day) together with a daily calendar.

Month 1 (+/- 1 weeks from randomization):

Phone contact in order to:

- record concomitant medications and record and evaluate adverse events;
- record self-reported compliance.

Month 3 (+/- 2 weeks from randomization):

Phone contact in order to:

- record concomitant medications and record and evaluate adverse events;
- record self-reported compliance.
- confirm date of the next schedule clinic visit and blood/urine tests
- CT scan if determined to be needed during multidisciplinary meetings

Participant will be asked to return used and unused boxes at the month 6 visit.

Month 6 (+/- 2 weeks from randomization):

- Participants will undergo physical exam, vital signs, weight, lab test (including  $\beta$ -HCG, if applicable) and biological sample collection (blood, urine) for biomarker measurement including TXB2.
- Concomitant medications will be recorded and adverse events will be recorded and evaluated.
- Compliance will be measured (subjects will be asked to return both used and unused bottles as well as calendar).
- CT scan if determined to be needed during multidisciplinary meetings

A 7-month supply of drug or placebo will be provided (a kit containing 7 bottles of drug or placebo, with 30 tablets in each bottle, 1 tablet per day).

Month 9 (+/- 2 weeks from randomization):

Phone contact in order to:

- confirm date of the next CT scan and month 12 clinic visit and ;
- record concomitant medications and record and evaluate adverse events;
- record self-reported compliance.

Month 12 (+/- 2 weeks from randomization):

- Participants will undergo physical exam, vital signs, weight, lab test and biological sample collection (blood and urine) for biomarker measurement including TXB2 and biorepository.
- Concomitant medications will be recorded and toxicity will be evaluated.

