### 7.6 Methods for Clinical Procedures

#### Assessment of lung nodules with low dose CT scan at IEO

Investigations will be performed with low-dose CT scans (average effective dose  $<1.5$  mSv, without contrast medium), with a multidetector (64 slices) CT scanner (CT750 HD/Optima 660, General Electric Healthcare, USA) with the following parameters:

- 120 Kvp, 30 mA
- Matrix 512x 512
- pitch 1.75
- 2.5 mm thickness
- Soft tissue algorithm
- single breath, in respiratory apnoea
- retro-reconstruction at 1.25 mm interval
- at the end of a session of 15 - 20 subjects the investigations will be sent to the workstation and archived both on hard-disk and on CD in DICOM format.

- multiplannar reconstruction and 3-dimensional volume reconstruction will be performed on the workstation (Advantage Windows 4.2, General Electric medical system)

Nodule volumes and volume doubling time (VDT) will be automatically calculated by Lung VCAR specific software (GE healthcare). In absence of available volumetry by the software, VDT will be calculated by the following formula using the maximum diameter.

$$VDT = \frac{\log_{10} 2 \times (\text{difference in days between first CT and second CT})}{3 \times \log_{10} (\text{difference in nodule size [mm] between first CT and second CT})}$$

Lung nodule maximum and mean density will be measured by the software lung VCAR (GE) before and after treatment.

Within 6 days an expert radiologist will read the images on the workstation through the windows for lung parenchyma (WW 1500, WL -650) and with MPVR (maximum projection visual resolution) reconstruction and mediastinum windows (WW 400, WL 40). A comparison between first year and baseline CT scan will be performed by Cosmos radiologists. All exams which show persistence of previous identified subsolid lung nodules will be discussed in a specific meeting with a senior radiologist (chemoprevention trial-responsible) and a senior thoracic surgeon (chemoprevention trial-responsible) within 10 days of the CT investigation. Eligible cases for the chemoprevention trial according to the criteria in section 4.1 and 4.2 are scheduled for the preliminary phone contact.

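### Section 5.4 says people with hyperuricemia or gout should not take aspirin, but no named entry criterion carries this over; only the opinion-based exclusion 4.2.9 can keep them out

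*Combined protocol and SAP*

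**What the plan says.** Section 5.4 (Contraindications) says: "People with kidney disease, hyperuricemia, or gout should not take aspirin". The reason it gives is reduced renal excretion of uric acid, which may make these conditions worse. The sentence carries no dose qualifier.

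Entry is decided on sections 4.1 and 4.2. Section 6.8 issues a randomisation number only after a site-level check, and once "eligibility has been confirmed by the site PI, and eligibility CRF has been entered into the DMI web application". Section 7.1 lists the baseline work as including "physical exam and medical history including baseline symptoms; concomitant medications; confirmation of eligibility criteria".

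The exclusions in 4.2 that come closest to the two conditions are:
- 4.2.1: "Subjects with chronic treatment (at least twice/week for more than 3 months) with Aspirin or other NSAIDs"
- 4.2.5: "Uncontrolled intercurrent illness including, but not limited to, ongoing or active infection", with further examples, none of them gout or hyperuricemia
- 4.2.9: "Participants who in the opinion of the PI will be at higher risk of ASA-related complications"

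Section 4.1.8 requires serum creatinine no higher than the institutional upper limit. Uric acid is neither in that list nor in the baseline laboratory panel in 7.2.

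**The concern.** Participants are asymptomatic and take the drug for a year for prevention, so the tolerance for avoidable harm is low. The protocol's contraindications section says that people with two common-enough chronic conditions should not take the drug, and why. The criteria that sites tick off before randomisation do not mention either condition. Whether such a person is kept out then depends on each PI recalling 5.4 and acting on it through a general clause. Two sites, or two investigators at one site, could decide the same case differently. What is at stake is the safety of a few individuals and a consistent answer to an eligibility question. The primary comparison is not at stake.

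**Working it through.** There is no figure in the plan to reproduce, so the first step is to set the texts side by side.

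**Step 1: conditions in 5.4 against named criteria in section 4.**

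| Condition in 5.4 | Strength in 5.4 | Named counterpart in 4.1 or 4.2 |
|---|---|---|
| NSAID allergy or intolerance | should not take | 4.2.2 |
| Bleeding tendency | should not take | 4.2.8 |
| Kidney disease | should not take | in part, creatinine limit in 4.1.8 |
| Gout | should not take | none |
| Hyperuricemia | should not take | none |
| NSAID-precipitated bronchospasm | caution | 4.2.8 |
| Peptic ulcer | medical advice first | 4.2.8, last 5 years |

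Mild diabetes, gastritis and G6PD deficiency also lack a counterpart, but 5.4 does not bar aspirin outright in those. Among the conditions with the strongest wording, gout and hyperuricemia are the two without a named criterion, even a partial one.

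**Step 2: can another criterion catch them?**
- 4.2.5 reaches uncontrolled illness, so at most an active flare.
- 4.2.1 reaches only those on chronic aspirin or NSAIDs.
- 4.1.8 reaches only those whose creatinine is raised.
- 4.2.7 lists barred drugs, but no urate-lowering drug is among them.
- 4.2.9 can reach any of them, by opinion, without reference to 5.4.

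A person with controlled gout or known hyperuricemia, normal creatinine and no chronic NSAID use therefore meets every named criterion. Only 4.2.9 is left.

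**Step 3: size.** Inputs: 64 per arm (sections 3 and 13.3). Consents C: about 150 (section 4.4), or 128/0.80 = 160, since 4.4 describes 128 as 80% of those consented. Prevalence p of known gout or hyperuricemia among people who otherwise qualify: 2-5%, an assumption with no source in the documents. Let a be the share of such people whom 4.2.9 would already remove.

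Expected number on aspirin = 64 × p × (1 − a). Extra consents from a named exclusion = C / (1 − p(1 − a)) − C.

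| a | On aspirin, p = 2% | On aspirin, p = 5% | Extra consents, C = 150 | Extra consents, C = 160 |
|---|---|---|---|---|
| 1 (always used) | 0 | 0 | 0 | 0 |
| 0.5 | 64 × 0.01 = 0.6 | 64 × 0.025 = 1.6 | 150/0.99 − 150 = 1.5 to 150/0.975 − 150 = 3.8 | 160/0.99 − 160 = 1.6 to 160/0.975 − 160 = 4.1 |
| 0 (never used) | 64 × 0.02 = 1.3 | 64 × 0.05 = 3.2 | 150/0.98 − 150 = 3.1 to 150/0.95 − 150 = 7.9 | 160/0.98 − 160 = 3.3 to 160/0.95 − 160 = 8.4 |

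The benefit and the cost move together. If 4.2.9 already removes everyone affected, a named exclusion protects nobody further and costs nothing. People removed by 4.1.8, 4.2.1 or 4.2.5 would lower p, and with it every non-zero figure.

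**The case against.** The strongest reply is that the protocol should be read as a whole. Section 5.4 is part of it, section 14.6 requires compliance with it, and the PI is responsible for giving the drug (5.2). Exclusion 4.2.9 is a numbered criterion, and 5.4 itself supplies the ground for using it. Site PI confirmation comes before every randomisation, and history and medications are taken at baseline, so known gout should be visible. Study staff must also sign an acknowledgement of the Investigator's Brochure or package insert (14.2.6). After entry, adverse events are reviewed at months 1, 3, 6, 9, 12 and 13, section 5.6 interrupts the drug for related toxicity of grade 2 or higher, and 8.3 lists a medical contraindication as a reason to stop. Finally, 5.4 reads in places like general aspirin information, and 4.2 was clearly not drafted as a copy of it.

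Much of this stands. A reader might infer that two rules contradict each other, or that the criteria positively admit these people. The documents do not support that: 4.2 is silent on the two conditions, no criterion calls for enrolling them, and 4.2.9 offers a route to exclusion. A reader might also take the sentence in 7.6, "Eligible cases for the chemoprevention trial according to the criteria in section 4.1 and 4.2 are scheduled", as proof that the final decision looks only at named items. That sentence concerns the IEO meeting that picks cases for a first phone call. It does not govern the final check at either site, and 4.2 includes 4.2.9 in any case.

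What does not stand is that nothing is left to fix. Exclusion 4.2.9 rests on opinion and does not cite 5.4, while the comparable conditions are at least partly named. Section 6.8 lists no separate check against 5.4. The toxicity and off-agent rules act only once dosing has begun, and for a grade 2 event judged possibly or probably related, 5.6 restarts the full dose after recovery with no exception for conditions in 5.4. If 5.4 is general text that is too broad for 100 mg/day, it still needs rewording.

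**Conclusion.** The point holds as a gap, and a minor one. An unqualified contraindication for hyperuricemia and gout has no named entry criterion, so exclusion depends on the PI's use of 4.2.9. At an assumed prevalence of 2-5%, 0 to about 3 of 64 aspirin participants are affected. The lower end applies if 4.2.9 is always used and the upper end if it never is; the documents do not say which is nearer the truth. It would be wrong to quote a fixed cost of about 3-8 extra consents for a named exclusion, because that ignores people whom 4.2.9 would have removed anyway; on the same assumption the range is 0 to about 8. The absence of any named criterion is read directly from the text and needs no assumption. Sample size, power and the analysis do not depend on it.

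**What to change.** Add one item to 4.2 and one field to the eligibility CRF: *history of gout or known hyperuricemia*. Ascertain it from the baseline medical history and from the concomitant medication CRF, which section 5.5 already has recording "start and stop date, dose and route of administration, and indication". In 4.2.9, add a cross-reference to 5.4 so that the remaining contraindications are considered in the same way at both sites.

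The cost is one criterion, one CRF field, one cross-reference and a few more screen failures, within the consent range above. No new test or visit is needed. The limit of this fix is that undiagnosed hyperuricemia would still be missed, because the baseline panel in 7.2 does not include uric acid.

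If the sponsor judges 100 mg/day acceptable in these conditions, the alternative is to reword that sentence of 5.4 as a caution at the study dose. That brings the sections into line with no extra consents, but it should be a stated decision.
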